The risk of non-response to tianeptine during the study period is addressed by having close clinical follow up of study subjects and stringent withdrawal criteria. These criteria are (1) participant withdraws his or her consent; (2) significant clinical worsening in the judgment of the study clinician; (3) a CGI-Improvement rating⁷ by the study clinician of 6 (worse) or 7 (much worse) for 2 consecutive visits; or (4) development of significant side effects or an adverse event grade 3 or higher. Any subject meeting any of these criteria will be withdrawn from the study and treated clinically. Furthermore, subjects may be withdrawn if they repeatedly miss scheduled appointments. If clinical worsening necessitates more intensive treatment, appropriate clinical care will be given but if possible the patient will still complete the ongoing assessments and final imaging visits.

Should a subject express suicidal ideation at any time during a study visit, the study clinician will be contacted immediately to assess the subject and to determine the appropriate course of action. Options for addressing suicidal ideation will include contacting the individual's mental health caregiver (if available), referring for urgent (same day) evaluation and treatment in an outpatient clinic, or emergency room evaluation and hospitalization. Similar practices will be used for other emergencies, including but not limited to psychosis, homicidal or violent thoughts, or an acute change in a subject's physical status.

2.8. Tianeptine taper and post-protocol treatment.

Once all study assessments are completed, subjects will be tapered off of tianeptine medication. Subjects will have their dosage reduced to 12.5 mg twice daily for two weeks, then 12.5 mg once daily for two weeks, and then tianeptine will be discontinued. Subjects will be assessed every two weeks in this post-protocol phase, with continuation of HRSD and CGI rating

scales. Appropriate clinical options will be discussed with any subject demonstrating worsening HRSD (≥ 16 on 24-item scale) or CGI (Improvement score ≥ 5 or Severity score ≥ 4 for two consecutive weeks) scores, most likely including initiation of FDA-approved antidepressant medication.

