4.2 Primary Safety Endpoints

The primary safety endpoint is:

Rate of serious adverse events (SAEs):

All SAEs will be assessed by a study physician to determine whether the relationship to the study procedures or treatment is considered to be likely, unlikely or unknown.

5. Statistical Plan

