6.1 Definitions

Adverse Event: *Adverse event* means any untoward medical occurrence associated with the use of a drug in humans, whether or not considered drug related.

Life-threatening adverse event or life-threatening suspected adverse reaction. An adverse event or suspected adverse reaction is considered "life-threatening" if, in the view of either the investigator or sponsor, its occurrence places the patient or subject at immediate risk of death. It does not include an adverse event or suspected adverse reaction that, had it occurred in a more severe form, might have caused death.

Serious Adverse Event: *Serious adverse event or serious suspected adverse reaction.* An adverse event or suspected adverse reaction is considered "serious" if, in the view of either the investigator or sponsor, it results in any of the following outcomes: Death, a life-threatening adverse event, inpatient hospitalization or prolongation of existing hospitalization, a persistent or significant incapacity or substantial disruption of the ability to conduct normal life functions, or a congenital anomaly/birth defect. Important medical events that may not result in death, be life-threatening, or require hospitalization may be considered serious when, based upon appropriate medical judgment, they may jeopardize the patient or subject and may require medical or surgical intervention to prevent one of the outcomes listed in this definition. Examples of such medical events include allergic bronchospasm requiring intensive treatment in an emergency room or at home, blood dyscrasias or convulsions that do not result in inpatient hospitalization, or the development of drug dependency or drug abuse.

Suspected adverse reaction means any adverse event for which there is a reasonable possibility that the drug caused the adverse event. For the purposes of IND safety reporting, "reasonable possibility" means there is evidence to suggest a causal relationship between the drug and the adverse event. Suspected adverse reaction implies a lesser degree of certainty about causality than adverse reaction, which means any adverse event caused by a drug.

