Unexpected adverse event or *unexpected suspected adverse reaction*. An adverse event or suspected adverse reaction is considered "unexpected" if it is not listed in the investigator brochure or is not listed at the specificity or severity that has been observed; or, if an investigator brochure is not required or available, is not consistent with the risk information described in the general investigational plan or elsewhere in the current application, as amended. For example, under this definition, hepatic necrosis would be unexpected (by virtue of greater severity) if the investigator brochure referred only to elevated hepatic enzymes or hepatitis. Similarly, cerebral thromboembolism and cerebral vasculitis would be unexpected (by virtue of greater specificity) if the investigator brochure listed only cerebral vascular accidents. "Unexpected," as used in this definition, also refers to adverse events or suspected adverse reactions that are mentioned in the investigator brochure as occurring with a class of drugs or as anticipated from the pharmacological properties of the drug, but are not specifically mentioned as occurring with the particular drug under investigation.

Adverse Event Reporting Period: The study period during which adverse events must be reported is normally defined as the period from the initiation of any study procedures to the end of the study treatment followup. For this study, the study drug follow-up is defined as 24 hours following the last administration of study drug (or the end of the study for those who must stop tianeptine but continue with the assessments).

Preexisting Condition: A preexisting condition is one that is present at the start of the study. A preexisting condition will be recorded as an adverse event if the frequency, intensity, or the character of the condition worsens during the study period.

General Physical Examination Findings: At screening, any clinically significant abnormality will be documented. At the end of the study, any new clinically significant findings/abnormalities that meet the definition of an adverse event will also be recorded and documented as an adverse event.

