6.2 Recording of Adverse Events

At each contact with the subject, the investigator will seek information on adverse events (AEs) by specific questioning and, as appropriate, by examination. Information on all adverse events will be recorded immediately in the source document. All clearly related signs, symptoms, and abnormal

diagnostic procedures results will be recorded in the source document. All adverse events occurring during the study period will be recorded. The clinical course of each event will be followed until resolution, stabilization, or until it has been determined that the study treatment or participation is not the cause. Serious adverse events that are still ongoing at the end of the study period will be followed up to determine the final outcome.

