6.4 Drug Related Risks

Tianeptine is generally well tolerated and severe side effects are rare.¹⁻⁵ Tolerability in comparative clinical trials has been generally found to be better than tricyclic antidepressants and comparable to selective serotonin reuptake inhibitors.¹⁻⁵ Commonly reported side effects with an incidence between 1 and 10% include the following:¹⁻⁶

Gastrointestinal: nausea, vomiting, flatulence, constipation, abdominal pain, dry mouth, loss of appetite

Psychiatric and Central Nervous System: headache, dizziness, altered dreaming, drowsiness, insomnia, presyncope, tremors

Cardiovascular: palpitations, chest pain, hot flashes, tachycardia

Respiratory: difficulty breathing

Musculoskeletal: muscle pain, lower back pain

General: feeling of weakness, feeling of lump in the throat

Extremely rarely, hepatotoxicity may occur, which is evidenced by increased liver enzymes and is fully reversible on drug withdrawal.⁷⁻⁹ Such liver toxicity appears to result from an immunoallergic response to the drug. To our knowledge, only 3 such cases have been reported in the literature. In contrast, the hepatic safety of tianeptine appears excellent in the vast majority of patients, even in instances of excessive consumption during abuse. For instance, a patient who became addicted to tianeptine and consumed doses of up to 1875 mg/day for over 5 months experienced no changes in hepatic toxicology parameters.¹⁰ Liver function tests will nonetheless be repeated at Week 4 to insure that levels are stable.

When used at the usual dosage of 37.5 mg/day, there is no development of physical or psychological dependence on tianeptine and no notable withdrawal symptoms on treatment cessation.¹⁻⁵ Rarely (1-3 per 1000)¹¹, abuse of tianeptine or dependence on the drug (when used at supratherapeutic doses) may occur. To account for this risk, we have planned for abuse risk mitigation by excluding patients with a history of opioid abuse, limiting drug distribution to 9-day courses provided at weekly clinical visits, and monitoring compliance at each clinical visit.

Drug Dependence and Abuse Potential:

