Accordingly, there is expected to be limited risk of dangerous overdose in the present study. Similarly, most chronic users of high-dose tianeptine do not experience serious toxicological complications (notably, no hepatotoxicity except in extremely rare cases) other than a withdrawal syndrome on discontinuation. In a long-term treatment study, 7 patients who attempted suicide by tianeptine overdose (dose of 150-500 mg, concomitant with alcohol or other psychotropic drugs) survived with favorable outcomes. Overdose has also been reported to be reversible with naloxone, consistent with agonist activity at MOR. To our knowledge, only 5 overdose deaths following tianeptine ingestion have been reported in the literature. In one case, tianeptine was the only intoxicant identified. However, the other cases were complicated by the identification of other psychoactive substances in the circulation of the decedents (one in combination with tramadol, one in combination with alprazolam, one a suicide in combination with alcohol, and one a suicide in combination with clomipramine and hydroxyzine).

To minimize risk patients with any history of opioid-use disorder or any history of moderate non-opioid (except nicotine) substance use disorder are excluded. Medication is distributed biweekly with a two week supply given and unused pills are collected at each in-person visit.

References

- (1) McEwen, B. S.; Chattarji, S.; Diamond, D. M.; Jay, T. M.; Reagan, L. P.; Svenningsson, P.; Fuchs, E. The Neurobiological Properties of Tianeptine (Stablon): From Monoamine Hypothesis to Glutamatergic Modulation. *Mol. Psychiatry* **2010**, *15* (3), 237–249.
- (3) Wagstaff, A. J.; Ormrod, D.; Spencer, C. M. Tianeptine: A Review of Its Use in Depressive Disorders. *CNS Drugs* **2001**, *15* (3), 231–259.
- (4) Preskorn, S. H. Tianeptine: A Facilitator of the Reuptake of Serotonin and Norepinephrine as an Antidepressant? *J. Psychiatr. Pract.* **2004**, *10*, 323-330.

(5) Wilde, M. I.; Benfield, P. Tianeptine: A Review of its Pharmacodynamic and Pharmacokinetic Properties, and Therapeutic Efficacy in Depression and Coexisting Anxiety and Depression. *Drugs* **1995**, *49* (3), 411-439.

(6) See the Summary of Product Characteristics (SmPC) included with this submission as Attachments E (original German) and F (English translation).

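### Serious adverse events that begin more than 24 hours after the last dose need not be reported or counted, no contact is stated after that dose, and the date on which the window closes is unclear

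*Combined protocol and SAP*

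**What the plan says.** Section 6.1 defines the adverse event reporting period. It opens with the first study procedure and closes at the end of treatment follow-up, and "the study drug follow-up is defined as 24 hours following the last administration of study drug". The same sentence carries an exception: "or the end of the study for those who must stop tianeptine but continue with the assessments". Section 6.2 ties recording to that period: "All adverse events occurring during the study period will be recorded". It also asks the investigator to question about adverse events at every contact, and it follows SAEs still open at the end of the period to their outcome.

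Section 4.2 makes the SAE rate the primary safety endpoint and gives it no time window. Section 6.1 includes "the development of drug dependency or drug abuse" among its examples of medical events that may be serious.

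Section 2.8 starts a four-week dose reduction after the study assessments are complete: "Subjects will be assessed every two weeks in this post-protocol phase, with continuation of HRSD and CGI rating" scales. Section 2.6 supplies tablets for this taper. The schedule table in Section 2.5 ends at Week 8, labelled as end of treatment, and has no taper or post-taper column.

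On withdrawal, Section 6.4 says that most chronic high-dose users have no serious toxicological complications "other than a withdrawal syndrome on discontinuation". For the usual dosage of 37.5 mg/day, which is the study dosage, it reports "no notable withdrawal symptoms on treatment cessation".

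**The concern.** The reporting rule sets what the primary safety endpoint can count. A first serious event two days after the final tablet falls outside the period, and the plan schedules no contact at which anyone would learn of it. The protocol describes the drug as a full mu-opioid agonist, treats dependency or abuse as potentially serious, and enrols people with treatment-resistant depression who are then taken off study drug. One day is a short observation period after cessation in that setting.

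The rule also closes reporting of all adverse events, not only serious ones, so later non-serious events are lost from the reports that go to the DSMB.

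Finally, a window anchored to the last dose is only as clear as the date of that dose, and the documents leave that date open.

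**Working it through.** The plan states no figure to reproduce on this point. The check sets sections side by side and does the timeline and tablet arithmetic, with day 0 as the first dose at Week 0 and the ±2-day visit allowance ignored.

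**1. Which window the endpoint uses.** Section 4.2 gives none. Section 6.2 records events in the study period, and Section 6.1 closes that period 24 hours after the last dose. The endpoint therefore inherits the 24-hour limit. The continued follow-up in Section 6.2 applies to SAEs already open when the period ends, not to new ones.

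**2. When the window closes.**
- Treatment before taper (Section 2.6): 8 × 7 = 56 days.
- Taper (Section 2.8): 14 + 14 = 28 days.
- If taper tablets are study drug: 56 + 28 + 1 = about day 85.
- If they are not: 56 + 1 = about day 57.

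The two readings differ by 28 days, the whole taper. The first is the more literal, because the study supplies the tablets. The second draws support from Section 2.8 calling the phase post-protocol and from the table labelling Week 8 as end of treatment. The documents do not say which applies.

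**3. Whether the last-dose date is clear.**
- Tablets needed for the taper in Section 2.8: 2 × 14 + 1 × 14 = 42.
- Tablets supplied for it in Section 2.6: 20.
- At two a day, 20 tablets last 20 / 2 = 10 days, which is 28 − 10 = 18 days short. The last dose would then fall about day 66 and the window would close about day 67.
- Spare tablets from the main supply: each 50-tablet pack covers 3 × 14 = 42, leaving 8. Four packs leave 4 × 8 = 32, and 20 + 32 = 52, which would cover 42. But Section 6.4 says unused tablets are collected at in-person visits.

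The two sections do not agree on supply and schedule, so the date that anchors the window is uncertain.

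**4. Who is covered after the last dose.**

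| Participant | Stated end of reporting | Stated contact after last dose |
|---|---|---|
| Completes treatment and taper | 24 hours after last dose | None |
| Stops tianeptine, continues assessments | End of study (Section 6.1 exception) | Remaining assessments |
| Withdrawn or dropped, leaves study (Sections 2.6, 2.7) | 24 hours after last dose | None, and no taper stated |

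Section 2.7 asks for continued assessments, if possible, where worsening calls for more intensive treatment. It does not extend this to the other reasons for withdrawal, nor does Section 2.6 for participants dropped for intolerance.

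**5. Adverse events during the taper.** Section 6.2 requires questioning at each contact, and taper visits are contacts. Section 2.8 names only HRSD and CGI for them, and the table in Section 2.5 does not show the phase. The duty exists in the text but is not visible in the schedule.

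**6. What cannot be computed.** The documents give no half-life, no time to onset of withdrawal and no post-cessation event rate. The share of events missed cannot be derived.

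**The case against.** The case for the plan has real force, and several stronger readings fail against it.

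- *A reader might infer that discontinuation events as a class fall outside the window.* On the literal reading the taper tablets keep it open, so events during both dose-reduction steps are inside. Only events starting more than 24 hours after the final tablet are excluded.
- *A reader might infer that events after cessation are never captured.* The exception in Section 6.1 follows to the end of the study those who stop the drug and stay in assessments. The supportable statement is that later events in the others need not be reported and no contact is stated.
- *A reader might infer that a withdrawal risk is expected at the study dose.* The syndrome in Section 6.4 is described in chronic high-dose users, and the same section reports none notable at the usual dosage. That is background, not a hypothesis or endpoint of this trial.
- *A reader might infer that the primary safety endpoint is missing withdrawal symptoms.* It counts serious events only, so most non-serious symptoms would stay out of it whatever the window.
- *A reader might infer from the schedule table that adverse events go unassessed in the taper.* The table has no taper column at all and so also omits the HRSD and CGI that Section 2.8 requires. Section 6.2 covers every contact. The HRSD suicide item and the worsening thresholds in Section 2.8 also mean the taper is not unmonitored.
- *A reader might want to put a number on the missed events.* Any rate would be an assumption without a source in the documents, as would a comparison with an expected SAE count.

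None of this supplies a contact after the last dose, covers participants who leave early, or settles whether the taper is study drug.

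**Conclusion.** The point holds in a limited form. The SAE-rate endpoint inherits a window that closes 24 hours after the last dose, except for participants who stop the drug and continue assessments. Serious events that begin later need not be reported or counted, and no contact is stated after the last taper dose. The clearest gap is among participants who are withdrawn or dropped early and leave the study.

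The closing date is uncertain by up to 28 days (about day 57 against about day 85) according to the status of the taper. The mismatch of 42 tablets needed against 20 supplied adds to this. These figures assume treatment and taper of the stated lengths.

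The size of any undercount is unknown. The conclusion rests on the stated reporting rule and on no assumption about how often withdrawal occurs at the study dose. The change is worth making because it is cheap and improves safety capture, not because a particular number of events has been shown to be lost.

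**What to change.** - Replace the 24-hour limit in Section 6.1 with a follow-up contact at a fixed interval after the last dose, for all participants including those who stop early. A telephone call suffices, and the sponsor's safety lead sets the interval.
- In Section 4.2, state that SAEs up to that contact count in the primary safety endpoint.
- State in Section 6.1 that taper tablets count as study drug for the reporting window.
- Add the taper visits and the post-dose contact to the table in Section 2.5, with adverse event assessment marked at each.
- Reconcile Sections 2.5, 2.6, 2.7, 2.8, 6.1 and 6.2, including the taper schedule against the tablets supplied for it. Which of those two is right is for the clinical team to settle.

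The cost is protocol wording, one short call per participant, slightly longer follow-up and possibly a few more reported events. Section 2.1 gives 28 of 75 participants as already entered, so 75 − 28 = 47 would be covered from enrolment. Since the window would then differ between earlier and later participants, the report should say which window applied to whom.

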6.2 Recording of Adverse Events

At each contact with the subject, the investigator will seek information on adverse events (AEs) by specific questioning and, as appropriate, by examination. Information on all adverse events will be recorded immediately in the source document. All clearly related signs, symptoms, and abnormal

diagnostic procedures results will be recorded in the source document. All adverse events occurring during the study period will be recorded. The clinical course of each event will be followed until resolution, stabilization, or until it has been determined that the study treatment or participation is not the cause. Serious adverse events that are still ongoing at the end of the study period will be followed up to determine the final outcome.

6.3 Reporting of Serious Adverse Events

6.3.1 IRB Notification by Investigator

Each SAE will be reported by the site within 24 hours to their IRB as well as to the IND sponsor by email to: [contact]. The site PI together with the IND sponsor will make the determination as to whether an incident, experience or outcome is likely to be the result of study procedures or treatment. The investigator must conclude in the SAE Report whether the protocol and/or consent form(s) should be modified as the result of the SAE. If the protocol and/or consent document(s) requires a revision, a modification must be submitted. At the time of continuing review of a protocol by each site's IRB, the site PI will submit a summary of all SAEs that occurred during the review period and since the beginning of the study, with a copy to the IND sponsor.

6.3.2 FDA Notification by Sponsor

The IND sponsor shall notify the FDA by telephone or by facsimile transmission of any unexpected fatal or life-threatening experience associated with the use of the drug as soon as possible but no later than 7 calendar days from the investigator's original receipt of the information. All other events that are considered to be serious, unexpected and possibly related to the study drug will be reported to the FDA within 15 calendar days. In addition, the IND sponsor will provide a summary of all SAEs in the annual reports submitted to the FDA.

